7.6 Causality Assessment of Adverse Events

For all AEs, the Principal Investigator will provide an assessment of causal relationship to the study treatment (active or placebo). The causality assessment must be recorded in the subject's source documents and on the AE eCRF. Causal relationship will be classified according to the following criteria:

1. *Unrelated*: The event is clearly due to causes other than the active study drug.

- 2. *Unlikely*: The event is doubtfully related to active study drug. The event was most likely related to other factors such as the subject's clinical state, concomitant drugs or other therapeutic interventions.
- 3. *Possible*: The event follows a reasonable temporal sequence from the time of active study drug administration, but could have been produced by other factors such as the subject's clinical state, therapeutic interventions or concomitant drugs.
- 4. *Probable*: The event follows a reasonable temporal sequence from the time of active study drug administration, and follows a known response pattern to the drug. The toxicity cannot be reasonably explained by other factors such as the subject's clinical state, therapeutic interventions or concomitant drugs.
- 5. *Definite*: The event follows a reasonable temporal sequence from the time of active study drug administration, follows a known response pattern to the drug, cannot be reasonably explained by other factors such as the subject's condition, concomitant drugs or therapeutic interventions, AND either occurs immediately following active study drug administration, improves on stopping the study drug, or reappears on re-exposure.

7.6.1 Potential Adverse Events Associated with ORMD-0801

Hypoglycemia and associated symptoms (e.g., weakness, dizziness, shakiness, increased sweating, palpitations, or confusion), have been associated with insulin administration, including ORMD-0801. Animal reproductive studies have not been conducted with ORMD-0801. It is not known whether ORMD-0801 can cause fetal harm when administered to a pregnant woman. It is also not known whether this product is excreted in human milk. Pregnant or breastfeeding women are excluded from this study.

Long-term animal studies have not been completed to assess whether ORMD-0801 impairs fertility.

7.7 Adverse Event Severity Assessment

The severity of each AE will be graded according to the NCI CTCAE, version 4.03. The severity of AEs that are not specifically listed in the CTCAE will be categorized according to the general guidelines provided in the CTCAE, and as summarized in the table below.

Table 2. General Guidelines for Severity Assessment of Adverse Events

Grade 1: Mild; asymptomatic or mild symptoms; clinical or diagnostic observations only; intervention not indicated.

Grade 2: Moderate; minimal, local or noninvasive intervention indicated; limiting age-appropriate instrumental activities of daily living (ADL) [preparing meals, shopping for groceries or clothes, using the telephone, managing money, etc.].

Grade 3: Severe or medically significant but not immediately life-threatening; hospitalization or prolongation of hospitalization indicated; disabling; limiting self-care ADL (bathing, dressing and undressing, feeding self, using the toilet, taking medications, and not bedridden).

Grade 4: Life-threatening consequences; urgent intervention indicated.

Grade 5: Death related to AE.

Page 53

Note the distinction between the severity and the seriousness of an AE. A severe AE is not necessarily a SAE. For example, a headache may be severe (interferes significantly with subject's usual function) but would not be classified as serious unless it met one of the criteria for SAEs, listed above in Section 7.4.

7.8 Expectedness of Adverse Event

An unexpected AE is defined in 21 CFR 312.32(a) as follows:

An AE is considered "unexpected" if it is not listed in the IB or is not listed at the specificity or severity that has been observed; or, if an IB is not required or available, is not consistent with the risk information described in the general investigational plan or elsewhere in the current application, as amended.

7.9 Assessment of Adverse Event Outcome

Outcome of AEs will be defined according to International Council for Harmonisation (ICH) Topic E2B, ICH Guideline.

- **Recovered/Resolved:** The subject has recovered fully from the AE without any remaining effects or impairment.
- **Recovered/Resolved with Sequelae**: The subject has recovered, but with an after effect possibly due to disease or treatment.
- Not Recovered/Not Resolved: The condition is still present.
- **Fatal:** Fatal should only be used when death is possibly related to the AE.
- Unknown: The primary outcome is not known at the time of the final assessment. If an outcome for an AE is not available at the time of the initial report, follow-up will proceed until an outcome is known or followed up to the Final Study Visit. Any subject with a possible study treatment-related AE at the Final Study Visit will be followed until resolution or stabilization of the event. Further, any SAE, whether or not related to Study treatment (active or placebo), that occurs within 30 days following the last dose of Study treatment will be followed until resolution or stabilization of the event.

7.10 Clinical Findings

Any significant clinical findings at the Follow-Up Visit will be followed until the condition returns to pre-study status, stabilizes, or can be explained as not being study treatment related. If the clinical finding is reported as an AE (per the criteria outlined in Section 7.5), the follow-up procedures for AEs defined above will apply.

8 STATISTICAL METHODS

This section describes the statistical methods to be used for the analysis and reporting of data collected under Protocol No. ORA-D-015. Additional details will be provided in the statistical analysis plan.

8.1 Study Design

The primary analysis is a comparison of change in HbA1c for the ORMD-0801 treated groups and placebo. Let pC be the delta HbA1C for the control (placebo) arm and let pT be the delta HbA1C for the treatment (ORMD-0801) arms. The primary analysis is:

H0: pC=pT

H1: pC < pT

Trial success is defined as rejecting the null hypothesis of no difference in delta HbA1C between active study drug and placebo.

In order to preserve on overall alpha level of 0.05, a stepwise approach will be used for hypothesis testing. The initial hypothesis will be ORMD-0801 TID versus combined placebo. If the initial hypothesis results in a rejection of H0, the secondary test, ORMD-0801 BID versus combined placebo, will take place. If both the initial and secondary hypotheses result in rejections of H0, the third test, ORMD-0801 QHS versus combined placebo will take place.

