Oramed has completed five Phase 1 safety studies of various formulations of ORMD-0801 in healthy human volunteers. Four Phase 2 studies have been completed, two in subjects with type 2 diabetes, and two in subjects with type 1 diabetes. These Phase 2 studies investigated different formulations, the effect of meals at different times following ORMD-0801 administration, and the effect of ORMD-0801 on glucose as measured by continuous glucose monitoring over a ten day treatment period with three doses per day prior to meals. One Phase 2 study assessed the safety and effectiveness on fasting blood glucose of repeat bed time administration of ORMD-

0801 in subjects with type 2 diabetes over a period of six weeks. In ORA-D-007, the difference in mean HbA1C in the ORMD-0801 combined group vs. the placebo group was statistically significant and at all doses tested, ORMD-0801 was as well tolerated as placebo and was not associated with any serious AEs related to the drug. More recently, ORA-D-012 (Phase 2a) evaluated the effect of ORMD-0801 on glucose (continuous glucose monitoring) administered qd, bid, or tid and concluded that there was a benefit to dosing multiple times per day. These studies demonstrated that the drug product is well-tolerated and can effectively reduce plasma glucose levels. There were no significant safety observations and no serious adverse reactions were reported for the completed studies, although there were two self-reported events of hypoglycemia in the 6-week, Phase 2 study.

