5.2 Randomization

Of the total 360 subjects, 265 subjects will be randomized to Cohort A and receive ORMD-0801 or placebo in one of 3 treatment regimens: QHS, BID, or TID. The actual treatment (ORMD-0801 or placebo) will be double-blinded to the subjects, investigators, monitors, and staff members responsible for treating and evaluating subjects, but the treatment regimen will be unblinded.

Creation, maintenance, and communication of the randomization scheme will be managed by an interactive web-based response system (IWRS). Subjects will be randomized 1:1:1 to QHS, BID, or TID and 1:3 (placebo:ORMD-0801) within each of those regimens at Visit 3. Therefore the overall randomization will be 1:1:1:1 (all placebo dosing regimens combined: ORMD-0801 QHS: ORMD-0801 BID: ORMD-0801 TID). Randomization will be in block sizes of 12 (1:3;1:3;1:3 [placebo QHS: ORMD-0801 QHS; placebo BID: ORMD-0801 BID; placebo TID: ORMD-0801 TID]).

An additional 75 subjects will be randomized to Cohort B and receive one of 5 treatment regimens (1:1:1:1): excipient matched placebo QHS, ORMD-0801 8 mg QHS, ORMD-0801 8 mg BID, ORMD-0801 16 mg QHS, or ORMD-0801 16 mg BID. Randomization will be in block sizes of 5 (1:1:1:1:1 [excipient matched placebo QHS: ORMD-0801 8 mg QHS: ORMD-0801 8 mg BID: ORMD-0801 16 mg QHS: ORMD-0801 16 mg BID]).

The randomization will be centralized and stratified by a) Sulfonylurea usage and b) whether they are on metformin alone or metformin plus one or 2 additional oral antidiabetic drugs at Screening. This will help ensure balanced treatment distribution of the subjects across the strata.

The additional 20 subjects in Cohort A who will receive excipient-matched placebo will not be randomized.

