8.2 Sample Size

8.2.1 Cohort A

The primary efficacy endpoint is the change from baseline in HbA1C at Visit 9 (Part 2- Week 10) after 12 weeks of active treatment. Based on previous results, a drop in HbA1C of 0.6% is expected with a standard deviation of 1.2. The primary analysis is based on combining the BID and TID treatment regimens together to compare to combined placebo. In order to achieve 80% power, there 48 completers are needed per treatment group.

Assuming an approximate 20% drop out rate, 240 randomized subjects would yield around 192 completers or approximately 48 subjects per treatment group. This would provide 80% power to detect a decrease in HbA1C of 0.6% for the BID and TID active combined versus combined placebo.

An additional 20 non-randomized subjects will be enrolled to receive excipient matched placebo to ensure that the fish oil placebo does not have a significant effect on efficacy or safety. The choice of adding 20 subjects is not based on statistical considerations.

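### Two different primary comparisons: the alpha-controlled sequence starts with TID alone, but the sample size and 80% power are for BID and TID pooled

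*Combined protocol and SAP*

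**What the plan says.** Section 8.1 sets the error control: "In order to preserve on overall alpha level of 0.05, a stepwise approach will be used for hypothesis testing". The order is then given: "The initial hypothesis will be ORMD-0801 TID versus combined placebo"; BID against combined placebo only if TID rejects; QHS against combined placebo only if both reject. No pooled comparison appears. Success is defined as rejecting the null hypothesis of no difference between active drug and placebo, without saying which of these nulls is meant.

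Section 8.2.1 says: "The primary analysis is based on combining the BID and TID treatment regimens together to compare to combined placebo". It assumes a drop of 0.6% with a standard deviation of 1.2, asks for 48 completers per group, and concludes: "This would provide 80% power to detect a decrease in HbA1C of 0.6% for the BID and TID active combined versus combined placebo". The enrolment behind it is: "Assuming an approximate 20% drop out rate, 240 randomized subjects would yield around 192 completers or approximately 48 subjects per treatment group". Section 5.2 has a different number: "Of the total 360 subjects, 265 subjects will be randomized to Cohort A".

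Sections 8.3 and 8.3.1 give the endpoint and the ANCOVA but name no treatment contrast. Section 8 adds only: "Additional details will be provided in the statistical analysis plan".

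**The concern.** The protocol declares two primary contrasts. One controls alpha and has no stated power. The other has the stated power and no place in the alpha control.

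TID is the gate. If it fails, BID and QHS cannot be tested, and the comparison used to size the trial cannot be claimed within the error control. If pooled BID+TID succeeds and TID fails, or the reverse, a protocol sentence supports either verdict. The primary analysis could then be chosen after the results are known, which a fixed sequence exists to prevent.

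**Working it through.** **Inputs.** Difference 0.6, SD 1.2, 48 completers per group, 240 randomised and 20% dropout (Section 8.2.1). Overall alpha 0.05, sidedness not stated (Section 8.1). Allocation 1:1:1:1 with placebo regimens combined, and 265 randomised (Section 5.2). Pooled BID+TID against placebo is therefore 2:1, and TID against placebo is 1:1.

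**Completers.** 240 × 0.8 / 4 = 48 per arm. 265 × 0.8 / 4 = 53 per arm.

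**Method.** Two-sample t-test: SE = 1.2 × √(1/n₁ + 1/n₂), noncentrality = difference / SE, power from the noncentral t distribution with n₁ + n₂ − 2 degrees of freedom.

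**The plan's own figure.** Pooled, 96 v 48: SE = 1.2 × √(1/96 + 1/48) = 0.212; noncentrality 0.6 / 0.212 = 2.83; power at two-sided 0.05 = 80.2%. The stated 80% reproduces. One-sided 0.05 would give 87.9%, so the plan's figure matches two-sided 0.05 (equivalently one-sided 0.025).

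**The gatekeeping test.** TID, 48 v 48: SE = 1.2 × √(2/48) = 0.245; noncentrality 0.6 / 0.245 = 2.45; power 67.9%. With 53 v 53: SE = 0.233; noncentrality 2.57; power 72.2%.

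The documents give no TID-specific effect, so a range is needed (two-sided 0.05):

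| Assumed TID effect | 48 per arm | 53 per arm |
|---|---|---|
| 0.5 | 52% | 57% |
| 0.6 | 68% | 72% |
| 0.7 | 81% | 85% |

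TID reaches 80% only if its effect is at least 0.69 (48 per arm) or 0.66 (53 per arm). If the pooled mean stays at 0.6, the BID effect is then 2 × 0.6 − 0.693 = 0.51, or 2 × 0.6 − 0.659 = 0.54.

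**How often the two primaries disagree.** One million simulated trials with a shared placebo arm, two-sided 0.05:

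| Assumed effects (TID, BID) | Per arm | Pooled rejects, TID does not | TID rejects, pooled does not | Both reject |
|---|---|---|---|---|
| 0.6, 0.6 | 48 | 14.6% | 2.3% | 65.6% |
| 0.6, 0.6 | 53 | 13.7% | 1.9% | 70.3% |
| 0.7, 0.5 | 48 | 5.5% | 6.2% | 74.5% |
| 0.7, 0.5 | 53 | 4.8% | 5.4% | 79.0% |

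At 48 per arm the verdicts differ in 14.6 + 2.3 = 16.9% of trials with equal effects, and in 5.5 + 6.2 = 11.7% with 0.7 and 0.5.

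**Two wording points, neither needed for the conclusion.** First, 265 + 20 + 75 = 360, the stated total, whereas 240 + 20 + 75 = 335. The 240 in Section 8.2.1 may be a calculated minimum; the larger number only raises power (pooled 84.0% at 106 v 53). Second, the alternative in Section 8.1 places pC below pT without defining the sign of the HbA1C delta. Under the Visit 9 minus Visit 3 convention of Section 8.3.1 it points the wrong way; if delta means the size of the drop, it is correct.

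**The case against.** **Sidedness.** The only alpha printed is 0.05, beside a directional alternative. Read as one-sided 0.05, TID at 0.6 has 78.4% power (48 per arm) or 81.9% (53 per arm), so little or no shortfall remains. That is fair as to size. But the pooled test would then have 87.9%, not the stated 80%, and the conflict over which contrast is primary stays.

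**ANCOVA.** The planned model adjusts for baseline HbA1C and background therapy. If SD 1.2 is unadjusted, an assumed baseline-to-change correlation of 0.3 to 0.5 multiplies it by √(1 − r²) and lifts TID power at 0.6 to 72–80% (48 per arm) or 76–84% (53 per arm). The plan does not say which SD it means. Its own 80% reproduces without any adjustment, so the comparison above is like for like, but any replacement figure should state the basis of the SD.

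**A larger TID effect.** The Introduction says an earlier Phase 2a study "concluded that there was a benefit to dosing multiple times per day". That may explain why TID is tested first, but no TID effect is given and the sample size does not use one.

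**The general hypothesis.** The null in Section 8.1 refers to the active arms collectively and could be read as pooled. Read that way it would include QHS, so it is not the BID+TID pool either.

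**A separate SAP.** It may settle the contrast, but its text is not in the file. Section 8 leaves it further detail only, and the protocol has already assigned the primary comparison twice.

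**Conclusion.** The concern holds and must be fixed before unblinding. Sections 8.1 and 8.2.1 name different primary contrasts, and nothing in the document reconciles them. That conclusion depends on no assumption about effect, SD or sidedness.

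The size does. With the plan's inputs, a two-sided 0.05 t-test and a TID effect of 0.6, the gatekeeping test has about 68% power at 48 per arm or 72% at 53, against the 80% stated for the pooled test. The gap closes if the TID effect is near 0.7, and narrows or closes if the test is one-sided at 0.05 or covariate adjustment reduces the SD enough.

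**What to change.** Before unblinding, state one primary contrast in Sections 8.1 and 8.2.1 and carry it into the SAP. The sponsor should choose between:

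- **(a) TID first.** Keep TID, BID, QHS. Delete the sentence that makes pooled BID+TID the primary analysis. Replace the 80% with the power of the TID test, giving its assumed effect, sidedness and the basis of the SD. At 0.6, two-sided 0.05 and an SD of 1.2 used without adjustment, this is about 68% at 48 per arm or 72% at 53.
- **(b) Pooled first.** Test pooled BID+TID, then TID, BID and QHS, each at two-sided 0.05. The pooled test has about 84% power with 265 randomised.

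Both control family-wise error across the Cohort A contrasts. Cohort B is outside the plan's sequence and outside both options.

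In either case, state that alpha is two-sided 0.05, as the 80% figure implies; reconcile 240 with 265 randomised (about 212 completers, 53 per arm); define delta as Visit 9 minus Visit 3 and align the alternative; and define success as rejection of the named primary null with the estimate favouring ORMD-0801.

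**Cost.** No extra patients. The change needs a protocol amendment, submitted to the regulatory authorities and approved by the IRB (Section 10). Option (a) means printing a lower power unless a larger TID effect is justified. Keeping TID first with 80% power at 0.6 would instead need 64 completers per arm, or 64 / 0.8 × 4 = 320 randomised. Option (b) costs TID some power because the pooled test must reject first: 67.9% to 65.6% (48 per arm) or 72.2% to 70.3% (53) with equal effects of 0.6; 80.7% to 74.5% or 84.5% to 79.0% with an assumed TID 0.7 and BID 0.5.

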8.2 Sample Size

8.2.1 Cohort A

The primary efficacy endpoint is the change from baseline in HbA1C at Visit 9 (Part 2- Week 10) after 12 weeks of active treatment. Based on previous results, a drop in HbA1C of 0.6% is expected with a standard deviation of 1.2. The primary analysis is based on combining the BID and TID treatment regimens together to compare to combined placebo. In order to achieve 80% power, there 48 completers are needed per treatment group.

Assuming an approximate 20% drop out rate, 240 randomized subjects would yield around 192 completers or approximately 48 subjects per treatment group. This would provide 80% power to detect a decrease in HbA1C of 0.6% for the BID and TID active combined versus combined placebo.

An additional 20 non-randomized subjects will be enrolled to receive excipient matched placebo to ensure that the fish oil placebo does not have a significant effect on efficacy or safety. The choice of adding 20 subjects is not based on statistical considerations.

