3 INVESTIGATIONAL PLAN

3.1 Overall Study Design and Plan

This study is designed to explore efficacy of ORMD-0801 when given in different regimens across a dose range for up to 12 weeks in subjects with T2DM. Approximately 360 subjects with type 2 diabetes will initially undergo a 2-week, single-blind placebo run-in period (Visits 1 and 3), followed by a 12-week treatment period (Visits 3 through 9). For Cohort A, the total 12-week treatment period will include a Part 1"dose escalation" interval (2 weeks) and a Part 2 stable dose "maintenance" interval (10 weeks, Visits 5 through 9). The stable dose interval will be sufficient to allow for a robust assessment of treatment effect based on the mean change from baseline in HbA1C (A1C). For Cohort B, the total 12-week treatment period will include a stable dosing period for both Part 1 (2 weeks, Visits 3 and 4) and Part 2 (10 weeks, Visits 5 through 9).

Single-Blind Placebo Run-in:

During the placebo run-in period subjects will self- administer blinded placebo study medication at night prior to bedtime (@ $10 \text{ PM} \pm 90$ minutes each night, no sooner than 2 hours after dinner). Outpatient glycemic levels and adverse events will be measured using SMBG and recorded in a diary.

Treatment Period:

Cohort A:

Of the total 360 subjects, 265 subjects will be randomized to one of the following four treatment arms:

- 1) ORMD-0801 once daily QHS: dosed in the evening prior to bedtime (@ $10 \text{ PM} \pm 90 \text{ minutes}$)
- 2) ORMD-0801 twice daily BID: dosed in the evening prior to bedtime (@ 10 PM \pm 90 minutes) and 30-45 minutes prior to breakfast.
- 3) ORMD-0801 three times daily TID: dosed in the evening prior to bedtime (@ 10 PM \pm 90 minutes) and 30-45 minutes prior to breakfast and lunch.
- 4) Matched Placebo (either OHS, BID, or TID)

In addition, per FDA request, the remaining 20 subjects will receive excipient matched placebo in a non-randomized single-blind fashion, TID, according to the same schedule as described above.

Cohort B:

Of the total 360 subjects, 75 will be randomized to one of the following four treatment arms:

- 1) ORMD-0801 8 mg once daily QHS: dosed in the evening prior to bedtime (@ 10 PM \pm 90 minutes).
- 2) ORMD-0801 8 mg twice daily BID: dosed in the evening prior to bedtime (@ 10 PM \pm 90 minutes) and 30-45 minutes prior to breakfast.
- 3) ORMD-0801 16 mg once daily QHS: dosed in the evening prior to bedtime (@ 10 PM \pm 90 minutes).

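### Section 8.2.1 bases its completers and power on 240 randomised Cohort A subjects, but the design randomises 265 and the extra 25 are not explained

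*Combined protocol and SAP*

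**What the plan says.** Section 8.2.1 sets out the Cohort A calculation. On the effect: "a drop in HbA1C of 0.6% is expected with a standard deviation of 1.2". On the contrast: "The primary analysis is based on combining the BID and TID treatment regimens together to compare to combined placebo". On the requirement: "In order to achieve 80% power, there 48 completers are needed per treatment group". On the number to randomise, at about 20% drop-out: "240 randomized subjects would yield around 192 completers or approximately 48 subjects per treatment group". The same section adds 20 non-randomised subjects on excipient-matched placebo.

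The sections that describe the conduct of the trial give a different number. Section 3.1: "Of the total 360 subjects, 265 subjects will be randomized to one of the following four treatment arms". Section 5.2: "Of the total 360 subjects, 265 subjects will be randomized to Cohort A". The Synopsis also has 265. All three set the 20 excipient-placebo subjects and the 75 Cohort B subjects apart from the 265, within a total of 360.

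Section 8.1 sets the overall alpha at 0.05 and writes the alternative hypothesis in one direction. Neither it nor Section 8.2.1 says whether the sample size assumes a one-sided or a two-sided test.

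**The concern.** Both 240 and 265 are described as subjects randomised in Cohort A, so they are two values for one quantity. The completers, the number per group and the power in Section 8.2.1 all follow from 240. If 265 are randomised at the drop-out rate the section assumes, none of those three figures describes the trial.

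What is at stake is the justification of the trial's main design number. An ethics committee or regulator who asks why 265 subjects are randomised finds a rationale for 240. The text does not say whether the other 25 reflect a higher power target, an allowance for greater loss, or a figure that was updated in some sections and not in this one.

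**Working it through.** **Inputs.** From Section 8.2.1: difference 0.6, SD 1.2, BID and TID pooled against combined placebo, 80% power, 20% drop-out. From Section 5.2: allocation 1:1:1:1 over four groups, so the pooled contrast is 2:1. From Section 8.1: overall alpha 0.05. Two-sided testing is my assumption, checked in step 1. Power is for an unadjusted two-group comparison among completers, which is how Section 8.2.1 counts.

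**1. Reproduce the plan's figure.** With n in the placebo group and 2n in the pooled active group:

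- n = (1.960 + 0.842)² × 1.2² × (1 + 1/2) / 0.6² = 7.85 × 6 = 47.1, rounded up to 48.
- Power at 96 v 48: SE = 1.2 × √(1/96 + 1/48) = 0.212; 0.6 / 0.212 = 2.83; 2.83 − 1.96 = 0.87; power 80.7% (80.2% from the t distribution).
- 48 × 4 = 192 completers; 192 / 0.8 = 240 randomised.

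The chain 48, 192, 240, 80% reproduces with two-sided 0.05. One-sided 0.05 would need only 38 per group, so two-sided is the reading that fits the text.

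**2. Do other components close the gap?**

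- 240 + 20 + 75 = 335, not 360.
- 265 + 20 + 75 = 360.
- 240 + 20 = 260, so counting the excipient-placebo subjects in Cohort A does not give 265 either.
- Randomisation is at Visit 3, after the run-in, so losses during the run-in cannot separate two counts of randomised subjects.
- Gap: 265 − 240 = 25; 25 / 240 = 10.4%.

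**3. Does another standard choice give 265?** Completers per group, multiplied by 4 and divided by 0.8:

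| Contrast and test | Completers per group | Randomised |
|---|---|---|
| 2:1 pooled, two-sided 0.05 | 48 | 240 |
| 2:1 pooled, one-sided 0.05 | 38 | 190 |
| 1:1, two-sided 0.05 | 63 | 315 |
| 1:1, one-sided 0.05 | 50 | 250 |

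None gives 265. In reverse, 265 × 0.8 / 4 = 53 completers per group, a target the protocol never states.

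**4. What 265 gives under the plan's own assumptions.**

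- 265 × 0.8 = 212 completers; 212 / 4 = 53 per group.
- Pooled BID and TID v placebo, 106 v 53: SE = 1.2 × √(1/106 + 1/53) = 0.202; 0.6 / 0.202 = 2.97.
- Two-sided 0.05: 2.97 − 1.96 = 1.01; power 84.4% (84.0% from the t distribution).
- One-sided 0.05: 2.97 − 1.645 = 1.33; power about 91%.

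**5. The test that Section 8.1 puts first.** TID alone v combined placebo, 53 v 53, same difference and SD: SE = 1.2 × √(2/53) = 0.233; 0.6 / 0.233 = 2.57; two-sided power is 73.0%, or 72.2% from the t distribution.

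**The case against.** The strongest reply is that Section 8.2.1 gives a minimum. It says 48 completers per group are needed and what 240 would yield; randomising 265 more than meets that. Every section that governs conduct uses 265, including the randomisation section, and 265 fits the total. On this view all that is missing is a sentence explaining a surplus.

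Much of this stands. It disposes of several stronger readings that a reader might infer:

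- **That the trial is underpowered because of the mismatch.** The difference runs the other way: 53 completers per group against 48 needed.
- **That sites cannot tell when Cohort A recruitment closes.** The number 240 appears only in the sample-size rationale. No operational section uses it.
- **That 265 must be wrong because it is not a multiple of the block size.** Section 5.2 says "Randomization will be in block sizes of 12", and 265 is 22 blocks plus one. It also stratifies by sulfonylurea use and by background therapy. Incomplete last blocks within strata are normal, so divisibility of the total shows nothing, and moving to 264 would not ensure complete blocks.
- **That the plan really expects 27.5% drop-out, since 1 − 192/265 = 27.5%.** That figure is obtained only by forcing 192 and 265 to agree. The stated rate is 20%, and Cohort B uses the same rate (75 enrolled, 60 completers).

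What the reply does not remove is the discrepancy. Section 8.2.1 does not present 240 as a floor to be exceeded by a stated margin; it gives 240 as the number randomised and attaches the completers and the power to it. Nor does describing the total as approximate explain an exact difference of 25 in one component.

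**Conclusion.** The point holds as an inconsistency in the figures that justify the sample size. Section 8.2.1 supports 240 randomised, 192 completers and 80% power; the design randomises 265, which at 20% drop-out means 212 completers and about 84% power for the contrast that section names. The 25 extra subjects have no stated basis.

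The consequence is limited. It does not reduce power for the pooled contrast or leave the operational target in doubt, and the correction is to text. It still merits making, because the number randomised and its stated power should agree.

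The 84% assumes a difference of 0.6, SD 1.2, 20% drop-out and two-sided alpha of 0.05. Sidedness is inferred from reproducing 48 per group; one-sided 0.05 would give about 91%. Nor should 84% be read as the power of the formal testing sequence, which opens with TID alone: that test has about 72% two-sided power at 53 per group on the same assumptions.

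**What to change.** Keep 265 and restate Section 8.2.1 as 265 randomised, about 212 completers (about 53 per group) at 20% drop-out, with about 84% power to detect 0.6% for pooled BID and TID against combined placebo. In the same sentence:

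- State the alpha and sidedness assumed (two-sided 0.05 gives 84%).
- Label the power as applying to the pooled contrast only, and not to the TID-alone test that opens the sequence in Section 8.1.
- Give the reason for choosing 265 over the 240 that the 80% target requires.

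If 240 is the intended number, leave Section 8.2.1 as it is on this point. Correct 265 in the Synopsis and Sections 3.1 and 5.2, and change the total from 360 to 335 wherever it appears.

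The cost of the first option is a few lines in one section, with no change to recruitment, the randomisation system or the analysis. The second touches more sections and lowers the recruitment target by 25. Neither adds subjects.
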